The proposed observational study will evaluate the relationship between measures of psychopathology, disordered eating, and impulsivity, (each assessed preoperatively and in the early postoperative period) and changes in weight and psychosocial status in the first two years after bariatric surgery. Secondary outcomes of prevalence and control of T2D and hypertension, health services utilization, and adherence to antidiabetes and antihypertensive medication will also be assessed. All participants will complete assessments at baseline (before surgery) and at 6, 12, and 24 months follow-up. Secondary aims will examine psychopathology, disordered eating, impulsivity, as well as weight loss, in relation to changes in eating behavior, physical activity, psychosocial status, and substance use in the first two years after bariatric surgery. The study has one specific aim and two secondary aims. Specific Aim 1: To determine the relationship between psychopathology, disordered eating, and impulsivity assessed preoperatively and changes in body weight over the first two years following bariatric surgery. We will determine which individual measures falling under these constructs are important in predicting the relative success of bariatric surgery. We will also examine the relationship of changes in the individual measures (from baseline to 6-months after surgery) on subsequent weight loss. (The study is powered on this aim.) We predict that individual measures of psychopathology, disordered eating, and impulsivity will predict smaller weight losses two years postoperatively. We also predict that smaller changes in measures of impulsivity, psychopathology, and disordered eating within the first 6 postoperative months will be associated with smaller weight losses at postoperative month 24. Secondary Aim 1: To examine the correlation structure among our individual measures, and subsequently will generate and confirm composite measures for the three constructs. Composite measures of psychopathology, disordered eating, and impulsivity will predict smaller weight losses two years postoperatively. We also will estimate the proportion of variance in weight loss accounted for by each composite measure. We predict that confirmatory factor analysis will confirm that our individual measures represent three constructs of psychopathology, disordered eating, and impulsivity. Higher values of these composite measures will in turn predict smaller weight losses at postoperative month 24. Secondary Aim 2: To assess the relationship between baseline measures of interest and postoperative changes in caloric and macronutrient intake, eating behavior, physical activity, and psychosocial status. We predict that participants with greater psychopathology, disordered eating, and impulsivity will report greater caloric intake, less favorable changes in macronutrient intake and eating behavior, participate in less physical activity and report more symptoms of psychosocial distress.

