however, are not universal and vary between patients and across surgical procedures. It is estimated that 20-30% of patients experience suboptimal weight loss or significant weight regain within the first few postoperative years. Reasons for this are not fully understood, but likely involve both physiological processes and behavioral factors (e.g., difficulty adhering to the dietary and physical activity recommendations made prior to surgery). Extreme Obesity More than one-third of American adults are obese, defined by a body mass index (BMI) of 30 kg/m2.1 Furthermore, 8.3% of women and 4.4% of men are extremely obese, defined by a BMI 40 kg/m2.1 Obesity, and extreme obesity in particular, is associated with major health complications including coronary heart disease, hypertension, type 2 diabetes mellitus, sleep apnea, and osteoarthritis.2-4 Surgical Treatment of Extreme Obesity Bariatric surgery is currently recommended for individuals 18 years and older with a BMI of 40 kg/m2 or those with a BMI of 35 kg/m2 in the presence of significant co-morbidities.5,6 Approximately 200,000 individuals are estimated to undergo bariatric surgery in the United States each year. The most common surgical procedures include the gastric bypass (GB), sleeve gastrectomy (SG), and adjustable gastric banding (AGB).7,8 As of 2013, the GB was the most common procedure in the United States, comprising 56% of all procedures; the SG comprised 36.3%.8 Anecdotal reports suggest that the SG is increasing in popularity while the AGB is now performed infrequently. With all three procedures, patients typically reach their maximum weight loss of 20-35% of body weight 12 months after surgery.3,4,9-16 These weight losses are associated with significant improvements in obesity-related co-morbidities and decreased risk of mortality.3,4,11,17-24 Despite these impressive results, studies have found that approximately 25% of patients who undergo bariatric surgery fail to reach or maintain the expected postoperative weight loss.25-27 Courcolous and colleagues, for example, observed that 23.6% of GB patients regained weight between postoperative year 1 and year 2. Less is known about the typical postoperative weight trajectory of patient who have undergone SG. Recent studies have suggested that weight regain is associated with deterioration of many of the health benefits seen with bariatric surgery.12,28-31 Psychosocial Status and Psychopathology in Candidates for Bariatric Surgery Extreme obesity is associated with a significant psychosocial burden, including impairments in quality of life, body image, sexual behavior and other areas of psychosocial functioning.32 While this distress is believed to contribute to the decision to have bariatric surgery, its impact on postoperative outcomes is less clear. At present, little is known about the physiological and behavioral contributions to success or failure of bariatric surgery.33 Regardless, weight regain after bariatric surgery is frequently attributed to preoperative psychosocial and behavioral factors.27,34-41 More specifically, there has been a great deal of interest in the presence of formal psychopathology in bariatric surgery patients and its potential contribution to postoperative outcomes.42-45 At least six studies have described rates of psychopathology in candidates for bariatric surgery using structured diagnostic instruments.46-51 Lifetime rates of any psychiatric diagnoses ranged from 36.8%-72.6%, higher than those reported in most studies of the general population. Mood disorders were the most frequent diagnoses, seen in 22.0%-54.8% of patients. Substance use disorders (SUDs) were found in up to 35.7% of patients and alcohol abuse or dependence in up to 33.2%. Binge eating disorder (BED), defined as eating an unusually large amount of food within a short period of time coupled with a loss of control over eating, has been diagnosed in 4.6% to 27.1% of patients. Current diagnoses (as compared with lifetime) were less common, reported in 20.9%-55.5% of candidates for surgery. Mood disorders were diagnosed in up to 31.5%. BED ranged from 3.4%-41.9%. Current substance use was seen in less than 2% of patients. (Note. The lower percentages of those with current psychopathology, as opposed to lifetime psychopathology, are expected.) While studies of the psychosocial characteristics of bariatric surgery candidates have been informative, they are not without limitations. Many studies have suffered from methodological concerns, including small sample sizes or lack of an appropriate comparison group. Further, establishing psychiatric diagnoses prior to bariatric surgery is challenging. Perioperative guidelines suggest that patients undergo an evaluation with a mental health professional prior to surgery3 and most third party payers require these evaluations. However, most programs do not use structured clinical interviews to establish diagnoses for clinical purposes.52,53 Several studies have suggested that candidates for bariatric surgery engage in impression management prior to surgery, in which they minimize reports of psychopathology to present themselves to the bariatric team in the most favorable light.54-56 To address this issue, assessment of psychiatric symptoms for research purposes is recommended to occur independently from the required clinical evaluation, as we will do in the proposed study. Nevertheless, studies focusing on the relationship between specific diagnoses and postoperative outcomes may fail to account for other psychological constructs that may be shared across diagnoses. Mood disorders, BED, and SUDs all share the common psychological construct of impulsivity, considered an important aspect of executive functioning. A lack of impulse control may contribute to the excessive weight gain seen in extreme obesity and may impact the results of bariatric surgery. Disinhibition and Impulsivity among Persons with Extreme Obesity Studies have suggested that individuals with obesity, and in particular those with extreme obesity presenting for bariatric surgery, show some deficits in executive functioning. For example, candidates for bariatric surgery have shown deficits in working memory, mental flexibility, motor speed and complex attention.57,58 These deficits could impact comprehension and retention of information presented to patients during the preoperative consultation process and, thus, negatively impact the ability to adhere to the dietary and behavioral changes required for an optimal postoperative outcome.45 At the same time, metabolic dysregulation, such as insulin resistance or hyperglycemeia seen in type 2 diabetes, also is associated with cognitive deficits, suggesting a potential physiological mechanism for the relationship.59-61 Dietary disinhibition, defined as a loss of control over eating, plays a central role in the overconsumption of food and, subsequently, the development of obesity.62.63 Disinhibition is similar to impulsivity, the term more commonly used in the substance use and smoking cessation literatures. Impulsivity is a multi-faceted construct and refers to the absence of the ability to inhibit an automatic behavior (otherwise known as response inhibition)64,65 and the tendency to discount future consequences in favor of more immediate outcomes (known as delay discounting).66,67 Similar to the role of disinhibition in obesity, impulsivity contributes to the development of and relapse with SUDs. Indeed, response inhibition and delay discounting are associated with both SUDs68-70 and obesity.71,72 Both also predict response to treatment for both SUDs73-75 and obesity.76 Chronic overeating and binge eating share several neurobiological and behavioral similarities with SUDs.77,78 In this regard, both may be viewed as behavioral disorders, in which intake (of food, alcohol, and/or drugs) escalates to a rate that is unhealthy and maladaptive. Nevertheless, the specific nature of the relationship between binge eating and substance use remains to be fully elucidated.79 There are similarities between binge eating and addictive disorders, including craving for the desired substance (drug or highly palatable food), a sense of loss of control when using, repeated attempts to control use despite clear adverse consequences, and the dedication of much time in obtaining and using the substance.80-82 Thus, the disinhibition observed with obesity and binge eating, the impulsivity seen with substance use disorders, and the emotional dysregulation associated with mood disorders all likely share commonalities (dashed lines in Figure 1) that may both contribute to the development of extreme obesity and also may be associated with weight loss (solid lines in Figure 1) and changes in psychosocial status after bariatric surgery. Psychosocial Status and Psychopathology after Bariatric Surgery In general, individuals who undergo bariatric surgery report dramatic improvements in psychosocial status and functioning postoperatively.83,84 The vast majority of patients report significant reductions in symptoms of depression and anxiety in the first postoperative year. They also report significant improvements in health and weight-related quality of life. Patients also report improvements in body image, sexual functioning, and relationship satisfaction.85-87 The relationship between preoperative psychopathology and postoperative outcomes is less robust.34,84 Livhits and colleagues reviewed this literature and concluded that the preoperative factors of BMI, BED, and the presence of personality disorders provided the strongest negative associations with postoperative weight loss.42 At least two studies have suggested that preoperative psychopathology, particularly mood and anxiety disorders, is associated with smaller weight postoperative weight losses.88,89 The relationship between BED and postoperative weight loss is unclear; some studies have found a relationship between preoperative BED and postoperative weight loss90.91 while others have not.92-94 Additionally, two studies have suggested that a history of substance abuse is associated with larger weight losses following bariatric surgery.95.96 The interpretation of this counterintuitive finding is that the selfregulation skills that help patients maintain their sobriety also help patients adhere to the demands of the recommended postoperative diet. Disinhibition and Impulsivity following Bariatric Surgery Encouragingly, studies have shown that there are improvements in executive functioning in persons with extreme obesity in the first two years after bariatric surgery.97,98 Postoperatively, patients typically report decreases in disinhibition and hunger, as well as increases in cognitive restraint.99,100 The physical aspects of bariatric surgery typically prevent individuals from eating the objectively large amount of food necessary to meet the diagnostic criteria of BED. However, many individuals continue to report the feeling of loss of control over their eating.44 The self-reported inability to control these impulses postoperatively is associated with smaller weight losses and greater emotional distress in the first few postoperative years.91,99,101,102 There is additional evidence that patients have difficulty with impulse control after surgery. A number of studies have suggested that there is an increased risk of substance abuse following bariatric surgery.101,103,104 King and colleagues,105 in their seminal investigation, found an increased rate of alcohol use disorder in the second postoperative year as compared to the year prior to surgery or in the first postoperative year. Other recent studies also have found increases in alcohol or composite substance abuse (drug, alcohol, or cigarettes) in the first two years after bariatric surgery.106-108 Postoperative substance use has been associated with smaller postoperative weight losses, postoperative nocturnal eating, and subjective hunger.109 Patients at

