
greatest risk for new onset SUDs were more likely to report problems with high sugar/low fat food before surgery, further suggesting the role of impulsivity in eating behavior and substance use before and after surgery.110 This increase in substance abuse after surgery has been described as addiction transfer111 and characterized as a modern example of symptom substitution in which abuse of one substance (food) is replaced by another (alcohol or drugs) when patients are unable to consume large amounts of food after surgery.109 A potential contributor to addiction transfer may be emotional dysregulation. In general, symptoms of depression typically improve within the first six months of bariatric surgery as patients are in the period of most rapid weight loss.35 Within the first two postoperative years, the use of anti-depressant medications also decreases; however, a substantial minority of patients report using these medications two years after surgery. As most patients begin to regain weight postoperatively, they also experience an erosion of the improvements in depressive symptoms and quality of life.112 In addition, a higher-than-expected number of postoperative suicides have been documented.17,44 A secondary aim of the proposed study will investigate the relationship between changes in weight during the first two postoperative years and changes in psychosocial status. Summary The relationship between preoperative psychosocial status and postoperative outcomes is one of the holy grail issues in the area of bariatric surgery. Concern about preoperative psychosocial status is one reason that standard clinical practice in the United States requires that individuals who seek bariatric surgery undergo a preoperative psychosocial evaluation (typically a clinical interview that does not include a structured diagnostic assessment) prior to surgery. This evaluation is designed to identify potential psychiatric and behavioral contraindications to surgery (psychosis; severe, untreated depression; active substance abuse; or significant behavioral non-compliance) and also provide patients with psychoeducation on the dietary and behavioral challenges after surgery.113 Prior to surgery, patients also meet with registered dietitians who teach them the basic elements of the postoperative diet and behaviors required for optimal postoperative outcomes. These evaluations exclude relatively few patients for surgery.55,84,114-116 Patients with psychosocial and behavioral issues, such as mood disorders and disordered eating, often are recommended for surgery even in the presence of these concerns. There is some evidence to suggest that a substantial percentage of these individuals subsequently experience smaller than expected weight losses, weight regain, or psychosocial distress after surgery. Patients with a history of psychopathology, specifically those with mood disorders or disordered eating, are vulnerable to returning to maladaptive eating and activity behaviors which likely promoted the development of extreme obesity and may compromise long-term weight control. While investigations of the relationship between specific diagnoses and postoperative outcomes have shed some light on these relationships, we believe that a common psychological construct, impulsivity--an important element of overeating, substance use, and mood disorders--may be a robust predictor of postoperative outcomes along with psychopathology or disordered eating. Few studies have used objective tests of impulse control in individuals undergoing bariatric surgery. To fill this gap, the proposed observational study will evaluate the relationship between measures of psychopathology, disordered eating, and impulsivity, (each assessed preoperatively and in the early postoperative period) and changes in weight and psychosocial status in the first two years after bariatric surgery. Results of this study would provide important information on the role of psychopathology, disordered eating, and impulsivity on outcomes of bariatric surgery and underscore the need for more comprehensive assessment and management of these behaviors before and after surgery.

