
The following documents are currently attached to this item:

There are no documents attached for this item.

Deception

Does your project use deception? No

Analysis Plan

Analysis will be conducted using Stata 13.0 (Stata Corporation, College Station, TX). After the completion of quality assurance procedures, descriptive statistics will be summarized for all patients by predictor group (dichotomized). Data screening: Prior to performing analyses, standard data screening/ cleaning procedures will be applied. These procedures will: screen the data for data-entry errors; check for outliers; assess the extent and pattern of missing data; create all summary scores needed for analysis; and check that appropriate assumptions of normality are met. In all analyses, the assumptions underlying the application of all the statistical methods that are used will be examined, principally through the use of standardized residuals, influence diagnostics, and graphical displays. Image processing will include image quality assessment procedures that examine global and region of interest (ROI) based raw and processed temporal signal-to-noise ratio, absolute and relative motion, and signal spike count. Potential outliers will be identified in the cumulative sample by examining quality assessment measures and flagging for further investigation subjects greater than two standard deviations from the mean on any one measure (i.e., behavioral performance, image distortion and artifact, general linear model fit). The purpose of this evaluation is to determine whether the time series is likely valid, and, if so, it will remain. Otherwise it will be corrected, if feasible, or removed from the analysis. The final sample will be examined in a similar fashion to determine whether any subjects warrant data cleaning or require exclusion from the final statistical analysis. Analysis of repeated measures: Our four-session within-subject design will generate multiple outcome measures that belong to the Gaussian family, and we will therefore use standard repeated-measures analysis of variance (ANOVA). Imaging outcomes (perfusion and BOLD) will be modeled using standard voxel-based image analysis techniques (described below) that incorporate random effects. Other outcomes (weight loss, ratings) will be modeled using a linear mixed-effects models framework, using using Stata 13.0 (Stata Corporation, College Station, TX). We could use a population averaged approach such as generalized estimating equations. However, the mixed model approach will provide the flexibility to allow for different error variances for different sessions if necessary. Voxel-based image analysis has limited flexibility, particularly when adding multiple covariates and interaction. When needed, summary values (e.g., mean rCBF, mean BOLD% signal change) extracted from ROIs will be modeled in STATAs mixed-models framework. These models can be extended to include additional explanatory variables (e.g., weight change, heart rate, respirations, age). Primary Aim 1 We will take a mixed models approach. The main interest in this study is the Group x Time interaction, where Group will be a between-subjects factor and Time will be a categorical within-subjects factor. This can be interpreted as population averages (GEE fitting method). Hypothesis 1: We will fit a 2 (Group: Dichotomized Baseline Measures, Low, High) x 3 (Time: change from baseline to month 6, 12 and 24) mixed-effects model for change in weight. Hypothesis 2: We will fit a 2 (Group: Dichotomized difference scores, 6 Month minus Baseline, Low, High) x 2 (Time: change from baseline to months 12 and 24) mixedeffects model for change in weight. In addition, the mixed effects models will include adjustments for surgical procedure, gender, and time since surgery. We recognize that the change in weight could also be associated with effects of several pertinent patient characteristics. To this end, we will consider additional covariates (e.g. sociodemographic variables, comorbidities, medication use, tobacco use, and initial weight). For both hypotheses, we will explore the continuous version of our predictor variables, where in place of Group, we use the real values of the predictor. This yields a difference of slopes with respect to predictor value across time points. Secondary Aim 1 We will use confirmatory factor analysis to verify our expected natural groupings of individual measures into composite measures. We will specify 3 factors and use Varimax rotation. We will assemble composite scores for each of our constructs by summing the standardized score values. We will then standardize the composite score and outcome (change in weight at 24 months). We will estimate the partial correlations (direct and indirect) among individual measures, composites, and outcome in a path analysis as suggested by Figure 1 to estimate the fraction of variance in outcome accounted for by each of the constructs. Secondary Aim 2 The outcomes will consist of (continuous) changes in behavior from baseline. We will use correlation to examine the relationship of baseline impulsivity measures to changes at 6, 12 and 24 months. The exception is changes in diet composition. In this analysis, we will use multivariate regression methods,

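### Hypothesis 2: the Group x Time interaction covers months 12 to 24 only, so it does not test the predicted difference in weight loss at month 24

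*Combined protocol and SAP*

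**What the plan says.** Specific Aim 1 (Overall objectives) has a second part: "We will also examine the relationship of changes in the individual measures (from baseline to 6-months after surgery) on subsequent weight loss". Its prediction is that smaller changes in the measures over the first 6 months "will be associated with smaller weight losses at postoperative month 24". The aim is described as the one on which the study is powered.

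The Analysis Plan, under Primary Aim 1, states: "The main interest in this study is the Group x Time interaction". That sentence covers both hypotheses. Hypothesis 1 uses three time levels (6, 12 and 24 months). Hypothesis 2 is a mixed-effects model for change in weight with "Group: Dichotomized difference scores, 6 Month minus Baseline, Low, High) x 2 (Time: change from baseline to months 12 and 24". No month-24 contrast and no Group main effect is named as the test. The listed adjustments and candidate covariates do not include weight loss over months 0 to 6.

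A continuous version of the predictor is to be explored: "This yields a difference of slopes with respect to predictor value across time points". The Weight paragraph under Procedures defines percent weight loss at every visit relative to baseline weight.

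**The concern.** The prediction concerns a level: the difference in weight loss between groups at month 24. The interaction concerns a change: whether that difference grew or shrank between months 12 and 24. Neither implies the other. If the interaction is reported as the test of Hypothesis 2, a real month-24 difference that had formed by month 12 would be recorded as no effect, and a difference that had vanished by month 24 could be recorded as an effect. If the month-24 contrast is reported instead, it will have been chosen without pre-specification.

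A second, smaller issue concerns the outcome. Weight change from baseline to month 12 or 24 includes months 0 to 6, the period over which the predictor itself is measured. For depression, the Background says that "symptoms of depression typically improve within the first six months of bariatric surgery as patients are in the period of most rapid weight loss". A measure that merely moved together with early weight loss could therefore show a month-24 association and be described as predicting later loss.

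**Working it through.** **Contrast algebra.** Let G(t) be the group gap in percent weight change from baseline at month t, taken as the less-improved group minus the more-improved group. A positive G means less loss in the group whose measure improved less, which is the predicted direction. With Time = {12, 24}:

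Group x Time = G(24) − G(12).

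Both terms subtract the same baseline, so it cancels, leaving the group difference in weight change from month 12 to month 24. The prediction concerns G(24). With the continuous predictor, the interaction is slope(24) − slope(12), so it has the same limitation.

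**Illustrative gaps (percentage points; not from the documents).**

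| Case | G(6) | G(12) | G(24) | Group x Time, G(24) − G(12) | Loss after month 6, G(24) − G(6) |
|---|---|---|---|---|---|
| a. Gap set by month 12 and kept | 3 | 5 | 5 | 0 | 2 |
| b. Gap set by month 6 and kept | 5 | 5 | 5 | 0 | 0 |
| c. Gap closes after month 12 | 5 | 5 | 0 | −5 | −5 |
| d. Gap opens late | 0 | 1 | 5 | 4 | 5 |

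In a and b the prediction, read as total loss, is true and the interaction is zero. In c the prediction is false and the interaction is not zero. Case b also shows that a month-24 gap measured from baseline need not involve any loss after month 6.

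**Size.** The plan states no power figure with inputs for this test, so there is none to reproduce. From the documents: N = 300 with completed baseline visits (Accrual). Assumed: a 150/150 split, no dropout, no covariates, two-sided alpha 0.05, SD 1 at each visit, and correlation ρ between the month-12 and month-24 changes of 0.6, 0.8 or 0.9.

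Power = Φ(δ/SE − 1.96) + Φ(−δ/SE − 1.96), where:
- Month-24 contrast: SE = √(2/150) = 0.1155. For δ = 0.4, δ/SE = 3.46 and power is 93%. For δ = 0.3 and 0.5 it is 74% and 99%.
- Interaction: SE = √(2(1−ρ)) × 0.1155. At ρ = 0.8 this is 0.632 × 0.1155 = 0.0730.

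With a month-24 gap of 0.4 SD, the interaction gives:
- Month-12 gap also 0.4: δ = 0, so it rejects 5% of the time whatever ρ is.
- Month-12 gap 0.3: δ = 0.1, δ/SE = 1.37 at ρ = 0.8, power 28% (16% at ρ = 0.6, 49% at ρ = 0.9).
- Month-12 gap 0.2: δ = 0.2, δ/SE = 2.74 at ρ = 0.8, power 78% (49% and 97%).

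With a gap of 0.3 SD at month 12 and none at month 24, δ/SE = 4.11 at ρ = 0.8. The interaction then rejects 98% of the time (83% at ρ = 0.6, over 99% at ρ = 0.9), while the month-24 contrast rejects 5%.

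A simulation of 4,000 studies with a constant 0.4 SD gap and ρ = 0.8 gave 93.1% for the month-24 contrast and 5.5% for the interaction.

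**The case against.** The strongest defence is that the notation is loose. The plan describes a four-session within-subject design. If baseline were the reference level of Time, the interaction terms would be the group differences in change from baseline to months 12 and 24, and one of them would be the contrast wanted. This fits poorly with a model written as 2 x 2 whose outcome is already change in weight. Even on that reading there are two interaction terms, and the plan does not say that the month-24 term decides the hypothesis. The defence lowers confidence somewhat but does not remove the need for a named contrast.

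It is also true that the fitted model can yield a month-24 contrast and that the sentence on main interest is general. The defect is therefore a missing pre-specification; the model itself can answer the question.

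Three stronger readings are tempting, and the documents do not support them:
- *The outcome is wrong because it must be loss after month 6.* The prediction is worded as losses at month 24, and Procedures measures percent loss from baseline at each visit. Leaving month 6 out of the outcomes also fits a sense of subsequent that means measured after the predictor. Total loss is the better-supported reading.
- *The interaction mainly measures regain.* The Background does say that "patients typically reach their maximum weight loss of 20-35% of body weight 12 months after surgery" and that "23.6% of GB patients regained weight between postoperative year 1 and year 2". But its opening paragraph places the main loss in the first 6 to 18 months, the regain figure is for gastric bypass only, and less is said to be known about sleeve gastrectomy. Months 12 to 24 may mix continuing loss, maintenance and regain.
- *Analysing loss after month 6 would drop patients without a month-6 weight.* That is avoidable with a suitable model, given under the fix.

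**Conclusion.** The point stands, with moderate to high confidence. On the natural reading of Hypothesis 2, the interaction that the plan makes its main interest is neither necessary nor sufficient for the month-24 difference that Specific Aim 1 predicts, and the exploratory continuous version shares the limitation. This follows from the two time levels alone and needs no assumed value. Likewise, a gap that is constant from month 12 to month 24 is rejected only at the alpha level, whatever the SDs or correlations.

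The other percentages, including 93% against 5% for a 0.4 SD gap, are illustrations. They rest on an even split, complete data, equal SDs and assumed correlations, for which the documents give no figures. How much power is lost in practice depends on how much of the month-24 gap is present by month 12.

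The conflict between subsequent loss and a baseline-anchored outcome is real but mainly one of wording.

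**What to change.** 1. For Hypothesis 2, pre-specify the group contrast at month 24 as the test (for the continuous predictor, its slope at month 24). Keep Group x Time as a secondary test of months 12 to 24.
2. State which weight loss is meant.
   - If total loss: keep the baseline-anchored outcome, remove *subsequent* from the aim, and describe the association as partly concurrent with the change in the measure.
   - If loss after month 6: fit Hypothesis 2 with the months 6, 12 and 24 already used for Hypothesis 1, and test the group difference in month 24 minus month 6. Under missing at random, which the plan already assumes, patients who have a change score but no month-6 weight stay in the model. Adjusting for weight loss over months 0 to 6 is a different estimand and can be a sensitivity analysis.
3. The sentence on main interest also governs Hypothesis 1, so check its wording at the same time.

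The cost is a few sentences in the Analysis Plan and, on the total-loss reading, one in the aim. Month-6 weight is already collected. The drawback of the post-month-6 reading is that the association will probably be smaller, because any part shared with early loss is removed.
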